#### 2.3.2 Other safety objectives

Other safety objectives will include assessment of hypoglycaemic events, cancers, peripheral oedema, laboratory tests, pulse, BP, waist circumference and body weight.

## 2.4 Exploratory objectives

Exploratory objectives include:

- Future biological research (optional), see Appendix H (does not apply to the People's Republic of China)
- Future genetic research (optional), see Appendix F (does not apply to the People's Republic of China)
- Collection of standard parameters used to assess glycaemic control. These include the change from baseline in HbA1c, FPG, homeostasis model assessment beta cell function (HOMA- $\beta$ ) and achievement of HbA1c  $\leq$ 6.5% and <7% (every year and end of the study visit).

# 2.5 Health economic and patient reported outcomes

Health economic data (hospitalisation information) and the patient reported outcome (PRO) of health-related quality of life data (gathered by using the EuroQol-5D questionnaire [EQ-5D]) will be compared between the 2 study arms (see Sections 6.5 and 6.9).

# 3. STUDY PLAN AND PROCEDURES

This Clinical Study Protocol has been subjected to a peer review according to AstraZeneca and Bristol-Myers Squibb (BMS) standard procedures.

# 3.1 Overall study design and flow chart

This is a multicentre, randomised, double-blind, placebo-controlled Phase IV study to evaluate whether treatment with saxagliptin can reduce the composite endpoint of CV death, non-fatal MI or non-fatal ischaemic stroke in patients with T2DM and to definitively exclude unacceptable CV toxicity. The anticipated duration of the study is approximately **4-5** years, including an anticipated enrolment period of 1-2 years and follow-up period of 3 years. However, the duration of the trial will be based on accrual of the predetermined number of events, and therefore the study may be shorter or longer.

Patients with documented T2DM and with either a history of previous CV events or multiple risk factors for vascular disease (see Section 4.1) will be enrolled from sites throughout the world. To reflect a scenario as close to real life as possible, both patients who are treated with glucose-lowering medication including oral antidiabetics and/or insulin (with the exception of incretin-based therapy) and treatment-naïve patients will be enrolled.

All patients will be treated to regional standards of care for cardiovascular risk factors (eg, blood pressure, lipids) and HbA1c. Investigators will be duly informed of this requirement via study aids and via information provided at Investigator's Meetings.

The study will focus on recruiting T2DM patients at elevated risk for CV events according to the two categories below:

- Patients with established CV disease (secondary prevention)
- Patients with multiple risk factors for CV events, but without established CV disease (primary prevention)

Further grouping of the patients will be based on their renal function (estimated GFR) according to the Modification of Diet in Renal Disease (MDRD) formula, (Levy et al 2006), see (Section 11.2.1):

- Normal renal function and mild renal impairment (estimated GFR >50mL/min)
- Moderate renal impairment (estimated GFR 30 to 50 mL/min)
- Severe renal impairment (estimated GFR <30 mL/min), excluding patients on chronic dialysis

Approximately **16500** patients meeting all eligibility criteria at approximately **900** study sites will be randomised (1:1) to receive either saxagliptin or placebo. Patients will be distributed as follows: at least 30% in North America, approximately 30% in Europe, and the remainder in South America, Asia, Australia, and South Africa.

Patients considered as primary prevention patients (ie, presenting with multiple risk factors for vascular disease but having no confirmed history of previous CV disease) will be capped at **approximately 3500 patients, or approximately 21%** of the total cohort. All potentially

eligible patients will undergo a combined screening/enrolment/randomisation visit. Each patient will sign an Informed Consent Form (ICF) and have screening evaluations performed.

At least 800 patients with moderate to severe renal impairment will be randomised into the study, approximately 300 of them with severe renal impairment. No more than approximately **15700** patients with normal renal function or mild renal impairment will be randomised to ensure that at least 800 patients with moderate to severe renal impairment are included. Once 300 patients with severe renal impairment are randomised, randomisation into this group will be stopped. The dose of saxagliptin is 5 mg in patients with normal renal function and mild renal impairment and 2.5 mg in patients with moderate and severe renal impairment (see Figure 4).

As all randomised patients will belong to the Intention To Treat (ITT) population and be part of the efficacy and safety analyses, it is important to avoid randomisation of non-eligible patients into the study (see Section 5.3).

During the randomised treatment period, diet and life-style modification will be reinforced.

An independent Data Monitoring Committee (DMC), a blinded independent Clinical Event adjudication Committee (CEC) (see Section 12.4) and Executive and Steering Committees (see Section 12.5) will be selected by the Sponsor and the academic leadership (TIMI Study Group and [name], Hadassah Medical Center).

The study plan, including enrolment/randomisation and follow-up visits, is outlined in Table 3. If the study would need to be prolonged to accrue the predetermined number of the primary endpoint events, visits and assessments will be added according to the same schedule as described in the study plan (Table 3).

Patients will return every 6 months for assessment of events related to the objectives of the study, tolerability and safety. Assessment of treatment compliance and provision of study drug will be done at these 6-month visits. In addition, phone contacts will be performed at a 3-month interval in between regular visits. Following the decision of the Executive Committee to close the trial, all Investigators will receive communication to complete an End-of-Treatment (EoT)/Closing Visit for patients still being treated with investigational product (IP), or a Closing Visit to capture any AEs and clinical events for patients who have prematurely discontinued IP. The latter patients should have completed the EoT visit in connection with the discontinuation of IP and subsequently attended the scheduled visits to capture any clinical events. Refer to Section 5.8.1 for details on procedures for discontinuing patients from IP.

Unless there is a scheduled visit within approximately 4 weeks after the date estimated by the Executive Committee as the end of the study, the Investigator/qualified designee will arrange for an EoT/Closing visit as soon after the estimated end-of-study date as possible.

All randomised patients, whether taking randomised IP or not, should be followed up at the end of the study at a minimum for CV events and survival. Survival based on publicly

available sources in cases where patients have withdrawn consent will also be investigated at the study end.

#### Visit 1 (0 month)

All potentially eligible patients will undergo a combined screening/enrolment/randomisation visit (may be performed during a period of 14 days) following their signed informed consent. If the patient has been clinically stable, HbA1c and serum creatinine values performed within the prior 6 months may be used to determine eligibility and treatment dose. If they have not been measured within 6 months, they should be performed as part of the screening assessments before randomisation to determine eligibility.

Following an 8-hour fast, the patients will have screening evaluations performed. Demography, medical history, and concomitant medication will be recorded. Women of childbearing potential will be tested for pregnancy. A physical examination and vital signs (pulse and BP), height and weight, waist circumference, as well as blood sampling for laboratory assessments of HbA1c, FPG, insulin, complete blood count (CBC) with differential, serum creatinine, total bilirubin (TB), alanine aminotransferase (ALT) and aspartate aminotransferase (AST), and limited urinalysis (for assessment of albumin and creatinine) will be done. Standard 12-lead electrocardiogram (ECG) readings will be recorded. Optional addenda to the informed consent for biological research and genetic research, respectively, will be obtained. The PRO questionnaire (EQ-5D) is to be completed. See Section 6.2 for further details on data collection. Patients who cannot complete the procedures required in the screening/enrolment/randomisation visit may split the visit and complete it within 14 days. Patients meeting all inclusion criteria and with no exclusion criteria will be randomised in a 1:1 ratio to receive either saxagliptin or placebo. Diet and life-style advice will be given.

#### **Telephone contacts every 3 months**

The patients will be contacted every 3rd month between regular site visits by the Investigator/study site personnel to record any AEs, suspected clinical events, IP status and use of concomitant medication. An unscheduled visit may be conducted as a result of the phone contact (eg, to follow-up on suspected clinical events).

#### **Short Message Service contacts**

In addition to standard telephone contact, patients will be asked to participate in use of a Short Message Service (SMS) technology to enhance the communication between the study site and the individual. The main purpose of this tool is patient retention because of the better "partnering" of the patient with the study site personnel. Permission from the patient to use this tool will be obtained by the study site. All patients will receive the same type messages within the major local language of their country of residence. This tool is not intended as a data collection tool.

The patient will receive messages such as 1) a reminder of their next visit; 2) reminder as to what to bring to their next visit (such as IP); 3) and messages of encouragement such as "Congratulations, you have just completed your first visit!" or "Happy Birthday".

#### Visits 2, 4, 6, 8 and 10 (6, 18, 30, 42 and 54 months)

Suspected clinical events and AEs will be recorded. Women of childbearing potential will be tested for pregnancy. IP will be returned and compliance assessed and new bottles of IP via the Interactive voice response system/Interactive web response system (IVRS/IWRS) will be dispensed. Concomitant medication will be recorded and diet and life-style advice will be given. If any event included in the composite endpoint of CV death, non-fatal MI or non-fatal ischaemic stroke has occurred since the previous visit, the EQ-5D will be completed.

#### Visits 3 and 7 (12 and 36 months)

Suspected clinical events and AEs will be recorded. If required, a targeted physical examination will be done. Vital signs (pulse and BP) as well as blood sampling (fasting not required) for laboratory assessments of HbA1c, CBC with differential, serum creatinine, TB, ALT and AST will be done. Women of childbearing potential will be tested for pregnancy. IP will be returned and compliance assessed and new bottles of IP via the IVRS/IWRS will be dispensed. The EQ-5D will be completed. Concomitant medication and weight will be recorded. Added assessments of urinalysis (microalbumin and creatinine) will be done. Diet and life-style advice will be given.

#### Visit 5 (24 months)

Suspected clinical events and AEs will be recorded. If required, a targeted physical examination will be done. Vital signs (pulse and BP) as well as fasting blood sampling for laboratory assessments of HbA1c, FPG, insulin, **lipids (Total-Cholesterol, LDL-Cholesterol, HDL-Cholesterol, and TG),** CBC with differential, serum creatinine, TB, ALT, AST as well as exploratory biomarkers will be done. Women of childbearing potential will be tested for pregnancy. IP will be returned and compliance assessed and new bottle of IP via the IVRS/IWRS will be dispensed. The EQ-5D will be completed. Concomitant medication will be recorded and diet and life-style advice will be given. Added assessments of urinalysis (microalbumin and creatinine), waist circumference and weight will be done.

#### Visit 9 (48 months)

Procedures according to Visit 3, with addition of limited urinalysis (for assessment of albumin and creatinine) will be done.

# End of Study - End of Treatment (EoT)/Closing Visit (anticipated at approximately 60 months or within 4 weeks after the closing date)

This visit should occur within approximately 4 weeks following the closing date as declared by the Executive Committee. **The actual time window will be determined by the global SAVOR operational team.** The anticipated time is at approximately 60 months. The time may be sooner or later as the study is event driven; hence, there cannot be a specified number assigned to this visit.

[figure not shown]
For patients on randomised treatment the procedures to be completed at the Closing Visit are the complete EoT procedures as described in Table 3. They comprise the following: recording of suspected clinical events and AEs, a targeted physical examination, vital signs (pulse and BP), weight, waist circumference as well as fasting blood sampling for laboratory assessments of HbA1c, FPG, insulin, **lipids (Total-Cholesterol, LDL-Cholesterol, HDL-Cholesterol, and TG),** CBC with differential, serum creatinine, TB, ALT and AST, and limited urinalysis (for assessment of albumin and creatinine), pregnancy testing of women of childbearing potential, completion of the EQ-5D questionnaire, recording of concomitant medication, and return of IP, including compliance assessment.

For patients who prematurely discontinued the randomised treatment, only AEs and suspected clinical events will be recorded at the Closing Visit. No further assessments are needed. The same is applicable for the other visits following the premature EoT, where the EoT assessments should be done at the time for discontinuation of treatment, if possible.

Clinical events are defined as all fatal events and all events comprised by the primary objectives (efficacy and safety) and the secondary efficacy objective (see Sections 2.1 and 2.2).

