#### Table 3Study plan

Activity	Enrolment/ Randomisation	Double-blind treatment period (anticipated to 60 months)									
Visit number 	1	2	3	4	5	6	7	8	9	10	EoT/ Closing visit 
Study month	0	6	12	18	24	30	36	42	48	54	
Serum creatinine 	Х		Х		Х		Х		Х		Х
Total bilirubin	Х		Х		Х		Х		Х		Х
Aspartate aminotransferase (AST [SGOT])	Х		X		Х		Х		X		X
Alanine aminotransferase (ALT [SGPT])	Х		X		X		Х		X		X
Lipids 					X						X
Patient reported outcomes EQ-5D questionnaire 	Х		X		Х		Х		X		X
Informed consent and blood samples for biological research 	Х				Х						
Informed consent and blood sample for genetic research 	х										
Adverse events and Clinical events 		Х	X	Х	Х	Х	Х	Х	X	X	X
Dispense investigational product through IVRS/IWRS	Х	Х	X	Х	Х	Х	Х	Х	Х	X	
IP compliance		Х	Х	Х	Х	Х	Х	Х	Х	Х	X
Diet and lifestyle advice	Х	Х	Х	X	Х	Х	Х	Х	X	Х	Х

 Every 3 months sites will perform a documented phone call with each patient to follow up on events, concomitant medication and adherence to treatment.
  At the close of the study all patients will return for the EoT/Closing Visit. Patients who prematurely discontinued IP need only to be assessed for AEs and clinical events. These patients should, if possible, have the EoT assessments at the time of their discontinuation from IP.

 Unscheduled visits may be done for safety lab follow-up, event follow-up or EoT in case of early discontinuation of IP.

39(94)

-  Visits will be repeated every 6 months and also phone calls every 3 months, according to the previous pattern until the Closing Visit as required. If the study needs to be prolonged to accrue the number of required primary endpoints, visits would be added, ie assessments according to Visits 9 and 10 may be repeated.
-  Targeted physical exam based on patient interview, AEs and laboratory results.
-  May be obtained within prior 21 days if patient is clinically stable.
-  Concomitant medication will be recorded according to Section 5.6.3.
-  Fasting blood samples will be taken at Visits 1, 5 and EoT. Other blood samples may be taken under non-fasting conditions. Analyses will be done at a central laboratory.
-  Estimated GFR will be estimated according to the Modification of Diet in Renal Disease (MDRD) formula.

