#### The next secondary efficacy endpoint is time to any documented death.

### 12.1.3.3 Other efficacy endpoints

Other efficacy endpoints include the time to the first event for the first 11 bullet points:

- Addition of new antidiabetic medication or  $\geq 1$  step increase in dose for an oral antidiabetic drug or  $\geq 25\%$  increase in insulin dose which lasts for  $\geq 3$  months
- Start of insulin regimen which lasts for  $\geq 3$  months
- Hospitalisation for hypoglycaemia
- CV death
- Non-fatal MI

- Non-fatal ischaemic stroke
- Hospitalisation for heart failure
- Hospitalisation for unstable angina pectoris
- Hospitalisation for coronary revascularisation
- Primary endpoint composite (CV death, non-fatal MI or non-fatal ischaemic stroke) occurring during the first year of follow-up and after the first year
- Documented laser treatment due to development of and/or deterioration in diabetic retinopathy
- Diabetic renal disease progression (diabetic nephropathy) as assessed by the following parameters:
  - Reduction from baseline of the microalbumin/creatinine ratio
  - Categorical change from baseline in albuminuria (normoalbuminuria, microalbuminuria, and/or macroalbuminuria)
  - Doubling of serum creatinine levels
  - Initiation of chronic dialysis and/or renal transplant and/or a serum creatinine >6.0 mg/dL (> 530 μmol/L)
- The composite event of death, doubling of serum creatinine, initiation of chronic dialysis, renal transplant, or a serum creatinine > 6.0 mg/dL (> 530 µmol/L)

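### After a patient stops IP, scheduled creatinine and urine albumin testing ends and the text conflicts on antidiabetic medication, so several other-efficacy endpoints are only partly observed

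*Protocol*

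**What the plan says.** Protocol Section 3.1, under the End-of-Treatment (EoT)/Closing Visit, states that for patients who stopped randomised treatment early "only AEs and suspected clinical events will be recorded at the Closing Visit. No further assessments are needed". It then widens the rule: "The same is applicable for the other visits following the premature EoT". The full EoT assessments are done once, when treatment stops, and only where this can be arranged. The scope is fixed in the same place: "Clinical events are defined as all fatal events and all events comprised by the primary objectives (efficacy and safety) and the secondary efficacy objective".

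Table 3 footnote 2 repeats this: "Patients who prematurely discontinued IP need only to be assessed for AEs and clinical events". Footnote 13 attaches the off-IP instruction to the row for adverse events (AEs) and clinical events. Sections 5.8.1 and 6.2.1 describe off-IP follow-up in the same terms.

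Section 12.1.3.3 lists the other efficacy endpoints. They include antidiabetic intensification, start of insulin, change in the albumin/creatinine ratio, albuminuria category, creatinine doubling, and dialysis, transplant or creatinine above 6.0 mg/dL. The last bullet is "The composite event of death, doubling of serum creatinine, initiation of chronic dialysis, renal transplant, or a serum creatinine" above 6.0 mg/dL. The section opens with "Other efficacy endpoints include the time to the first event for the first 11 bullet points".

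On concomitant medication there are two messages. Table 3 footnote 1 has a documented 3-monthly call to each patient that covers it, and the telephone-contact paragraph of Section 3.1 likewise makes no exception for patients off IP. The Closing Visit text leaves it out once IP has stopped. The telephone list in Section 6.2.1 flags only clinical events as continuing for those patients.

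**The concern.** Stopping IP happens after randomisation and can differ between arms. If the measurements that define an endpoint end when IP ends, what is observed depends on treatment behaviour, and randomisation no longer protects the comparison. Patients who stop IP are also likely to have their background glucose-lowering regimen changed, so time to intensification and time to insulin are exposed.

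The renal composite has a further problem. Its components are followed for different lengths of time: death to study end in everyone, scheduled creatinine only until IP stops. A statistical analysis plan can choose a censoring rule, but it cannot recover data that sites were told not to collect.

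**Working it through.** No stated figure underlies this point, so there is none to reproduce. The check is a comparison of texts, followed by an illustration of scale.

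**1. What each endpoint needs, and what remains off IP**

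| Item in Section 12.1.3.3 | Data needed | Route after IP stops |
|---|---|---|
| Albumin/creatinine ratio, albuminuria category | Scheduled urine sample | None after EoT |
| Creatinine doubling, creatinine >6.0 mg/dL | Scheduled serum creatinine | None scheduled; incidental AE report only |
| Dialysis, transplant | Event report | AE or serious AE (SAE) reporting |
| Death (in the composite) | Vital status | Complete; Section 3.1 seeks survival for all randomised patients |
| Antidiabetic intensification, insulin start | Medication record | Contradictory |

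**2. Can AE reporting replace scheduled creatinine?** Section 6.4.3 has deterioration in protocol-mandated laboratory values reported as an AE only if it meets a seriousness criterion or led to stopping IP. Section 6.4.1.1 and Appendix I Section 10 do treat renal abnormalities, including creatinine doubling, as events of special interest with supplemental pages. That route works only if someone has measured creatinine outside the protocol. An asymptomatic doubling would usually be missed.

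**3. Censoring.** Section 11.1 censors at last documented contact, but states this for the primary and secondary endpoints. If the same rule were carried over to the creatinine endpoints, off-IP time without a sample would count as event-free.

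**4. Time-to-event list.** Counting the bullets in Section 12.1.3.3, laser treatment is the 11th, diabetic renal disease progression the 12th and the renal composite the 13th. Creatinine doubling and dialysis/transplant sit under the 12th. All three are events, and all fall outside the first 11.

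**5. Scale (assumed rates).** The protocol gives no IP-stop rate. The 2.8% per year in Section 12.3 is discontinuation from the study, a different quantity. Mean follow-up from Section 12.3 is 3 years plus half of 15 months, 3 + 0.625 = 3.625, taken as T = 3.6 years. With a constant stopping rate r and no restarts:

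- share ever off IP = 1 − exp(−rT)
- share of person-time off IP = 1 − [1 − exp(−rT)]/(rT)

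| Assumed r per year | rT | Ever off IP | Of 16500 | Person-time off IP |
|---|---|---|---|---|
| 3% | 0.108 | 10% | about 1700 | 5% |
| 5% | 0.180 | 16% | about 2700 | 8% |
| 7% | 0.252 | 22% | about 3700 | 12% |
| 10% | 0.360 | 30% | about 5000 | 16% |

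Section 5.8.1 encourages restart, and Section 6.2.1 returns restarted patients to the full schedule, so for any given r these figures are upper values.

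**The case against.** The strongest reply is that this is a deliberate simplification in an outcome trial of 16500 patients. The primary composite, the secondary composite and mortality are all followed off IP. The affected variables lie outside the alpha-controlled sequence in Section 12.2.3, and censoring for them commonly belongs in the analysis plan. Dialysis and transplant keep a reporting route. The opening sentence of Section 12.1.3.3 says that the endpoints include time to first event for 11 bullets, which does not exclude others.

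Most of that stands, and it limits the weight of the point. It does not answer the loss of systematic creatinine and albuminuria data, which no later document can repair, or the conflicting instructions on medication.

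Several stronger readings are tempting but not supported:

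- **That medication recording plainly stops off IP.** Table 3 footnote 1 and the Section 3.1 telephone paragraph say otherwise; the text is inconsistent.
- **That the intention-to-treat principle is contradicted.** Section 3.1 does say "As all randomised patients will belong to the Intention To Treat (ITT) population and be part of the efficacy and safety analyses", but that sentence is about not randomising ineligible patients. Section 12.1.1, which defines the analysis set, ties it to the primary and secondary objectives.
- **That EQ-5D is a lost efficacy endpoint.** Section 2.5 classes it as a patient-reported outcome alongside the health economic data.
- **That the composite should be cut off at the last creatinine.** This would discard later deaths, dialysis and transplants, and would build in the informative censoring that is the worry here.

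**Conclusion.** The point holds for a limited set of endpoints. After premature IP discontinuation, scheduled creatinine and urine albumin/creatinine end at a single EoT assessment that may not take place, although listed efficacy endpoints depend on them. The renal composite then combines complete capture of deaths, event-report capture of dialysis and transplant, and incidental capture of creatinine events. The instructions on antidiabetic medication off IP cannot all be followed.

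A reader might infer that these endpoints cannot be analysed at all. An analysis of data up to the EoT assessment remains possible, but it would be an on-treatment analysis and should be described as one.

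The primary, secondary and mortality endpoints and the sample size are untouched. The illustrated 10-30% of patients and 5-16% of person-time off IP rest on an assumed 3-10% per year, a constant rate and no restarts. The person-time share does not mean that every endpoint is blank for that time. The change is worth making because it is cheap and lowers bias in the intensification, insulin and renal endpoints.

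**What to change.** - Reconcile the Closing Visit text in Section 3.1, Table 3 footnotes 1, 2 and 13, and Sections 5.8.1 and 6.2.1, so that antidiabetic medication changes and insulin start are recorded at the visits and 3-monthly calls already scheduled for patients off IP.
- Keep the annual central serum creatinine and urine albumin/creatinine sample for off-IP patients who attend in person.
- Where no later sample exists, report laboratory-based endpoints with follow-up stated to end at the last laboratory assessment. Keep later deaths, dialysis and transplants in the composite.
- In Section 12.1.3.3, add the renal composite, creatinine doubling and dialysis/transplant to the time-to-first-event list.

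The cost is amendment wording, existing case report form pages left open for patients off IP, and one routine blood and urine sample a year for those who attend. Site burden rises modestly.
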